4.4.2. Male Contraception

Male participants must agree to take all necessary measures to avoid causing pregnancy in their sexual partners during the study and for 3 months after the last dose of investigational product. Medically acceptable contraceptives include surgical sterilization (such as a vasectomy) and a condom used with a spermicidal gel or foam. The female partner of a male subject must use hormonal oral contraceptives when the male subject uses a condom. Contraceptive measures such as Plan B™, sold for emergency use after unprotected sex, are not acceptable methods for routine use.

Male subjects should not donate sperm during the study and for 30 days after the last dose of investigational product.

4.5. Discontinuation of Subjects

A subject may withdraw — or their parent/LAR may withdraw the subject — from the study at any time for any reason without prejudice to their future medical care by the physician or at the hospital. The investigator or sponsor may withdraw the subject at any time (e.g., in the interest of subject safety). The investigator is encouraged to discuss withdrawal of a subject from investigational product with the medical monitor when possible.

Subjects who discontinue investigational product treatment before the completion of the double-blind phase will continue to be followed per protocol and at minimum maintain daily seizure eDiary entry until the double-blind phase is completed. These subjects should also return to the site after the taper for safety follow-up assessments.

If the investigational product is discontinued at any time, subjects should follow the 2-week taper schedule. If the subject discontinues during the open-label phase, evaluations listed for Taper Visit are to be performed as completely as possible. Whenever possible, all subjects who discontinue should also undergo the protocol-specified Safety Follow-up Post Taper visit. Comments (spontaneous or elicited) or complaints made by the subject must be recorded in the source documents. The reason for termination, date of stopping investigational product, and total amount of investigational product taken must be recorded in the electronic case report form (eCRF) and source documents. Discontinuation of investigational product due to AEs must also be reflected on the AE eCRF page.

4.5.1. Subject Withdrawal Criteria

All subjects or his/her parent/LAR reserve the right to withdraw from the clinical study at any time, as stated in the informed consent form. The investigator may discontinue subjects from the clinical study for any of the following reasons:

- Subject is found to have entered the study in violation of the protocol;
- Subject requires the use of a disallowed concomitant medication;
- Subject's condition changes after entering the clinical investigation so that the subject no longer meets the inclusion criteria or develops any of the exclusion criteria;
- Subject or parent/LAR withdraws consent or assent to participate in the study;
- Subject is noncompliant with the procedures set forth in the protocol;

- Subject experiences an AE/SAE that warrants withdrawal from the study;
- Laboratory, medical, or clinical finding for which clinical intervention should take precedence over study participation; or
- It is the investigator's opinion that it is not in the subject's best interest to continue in the study.

Decisions to discontinue the study will be made at each participating site by the PI. If feasible, the reason for discontinuation should be discussed with the sponsor's medical monitor prior to subject discontinuation. Subjects who discontinue investigational product during the double-blind phase will continue to record daily seizure frequency at minimum until the completion of the double-blind phase.

If a subject must be abruptly discontinued from the investigational product (e.g., severe rash), careful attention should be paid for the possibility of withdrawal symptoms such as increase in seizure number or severity. Consideration should be made by the investigator for providing another GABA-A medication for 1-2 weeks such as clobazam to mitigate the potential risk of withdrawal from a positive modulator of GABA-A.

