7.2.2.3. Telephone Follow-up Visit (Weeks 11, 13 ± 3 days)

A telephone follow-up visit will be conducted at Weeks 11 and 13 to assess the following:

- Adverse events
- Seizure and medication diary review

7.2.3. Final Double-blind Visit /First Open-label Visit (Visit 5, Week 17 ± 3 days)

The following study procedures/assessments will be completed during the final double-blind visit or taper visit or at the time of early termination:

- Vital signs (to include BP, HR, RR, body temperature, and weight)
- Physical, neurological, and developmental examination
- ECG
- Clinical laboratory tests (to include CBC with automated differential, creatinine, blood urea nitrogen, and comprehensive metabolic panel)
- Urinalysis
- Investigational Product PK
- Concomitant AED review and levels if per SOC
- Neurosteroid level sample draw
- Adverse events
- Seizure and medication diary review
- CGICA
- CGI-C (parent/caregiver/LAR identified behavioral target)
- CGI-I (parent/caregiver/LAR and clinician)
- CGI-CSID
- EEG
- CSHQ

- ADAMS
- QI-Disability
- PSI
- Dispense investigational product

7.2.4. Telephone Follow-up (3 days after Visit 5 \pm 1 day, Weeks 18 and 20 \pm 3 days)

A telephone follow-up visit will be conducted 3 days after Visit 5 and at Weeks 18 and 20 to assess the following:

- Adverse events
- Seizure and medication diary review

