9.7.2. Key Secondary Efficacy Endpoints

The key Secondary endpoints are:

- Number (%) of subjects with a $\geq 50\%$ reduction from baseline in primary seizure frequency.
- Clinical Global Impression of Improvement (CGI-I) at the last scheduled visit in the 17-week DB treatment phase.

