### 7.1 Double-Blind Phase

All efficacy analyses will be conducted in the ITT population. A supportive analysis of the primary and secondary efficacy endpoints also will be conducted in the PP population.

The estimand that is most clinically relevant as well as estimable in a manner that protects the integrity of randomization is the outcome measure (e.g., the percent change in 28-day seizure frequency), where ALL randomized subjects would be included in this analysis throughout the study period. Hence, all available data will be used, even if they were collected after the subject stopped taking study medication, regardless of whether the subject took rescue medication. [Section 7.1.1](#) details the handling of missing data.

For the analyses of seizures, the baseline phase consists of 6 weeks before the first day of treatment and the DB phase starts the day following the first day of DB treatment until the final visit for subjects who do not enter the OLE and up to the day before the first dose of OLE treatment for those who do. The first day of treatment is not in either phase since the seizures could occur both before and after the first treatment.

Tests of significance between the 2 treatment groups will be performed for the primary endpoint with a 2-sided significance level of 0.05.

Seizure diary compliance for the baseline and the post-baseline DB phase intervals will be calculated as:

$100 \times (\text{Number of Days with Available Seizure Diary}) / (\text{Last Available Seizure Diary Date} - \text{First Day of the Phase} + 1)$ .

Seizure diary compliance between visits will be calculated as:

$100 \times (\text{Number of days with available seizure data between visits}) / \text{Number of days between visits}$ , with the days between visits defined as the day of the prior visit up to the day before the current visit.

The compliances will be summarized with descriptive statistics and the percentage of subjects at least 80% compliant.

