### 7.1.1 Handling of Missing Data

The primary analysis will use all available data. Careful educating and monitoring of the study sites will attempt to limit the amount of missing data to nearly zero, but despite these efforts, some missing data may still arise. Thus a sensitivity analysis, in which the missing data will be replaced, will be performed on the primary efficacy endpoint; see [Section 7.1.8](#).

When an item from a secondary or efficacy endpoint is missing, then so will any subscales or totals that include it.

When subjects prematurely discontinue from the study they are asked to complete the non-seizure assessments at the Taper Visit. For analysis purposes, their data from the Taper Visit will be reassigned to the first visit at which the assessment is scheduled subsequent to the discontinuation and the scheduled day is within 32 days of the Taper visit. For example if a subject completed Visit 3 and then prematurely discontinued and completed assessments at the Taper Visit on Study Day 100, then the Taper visit would be reassigned to Visit 5 (Week 17) for analysis purposes since Visit 5 is scheduled for Study Day 120, 20 days after the assessments were actually completed. (Although the first visit after Visit 3 is Visit 4 (Week 9), that visit is scheduled on Study Day 64, which is not within 32 days of Study Day 100.) But if the Taper Visit assessments were completed on Study Day 28 then the Taper visit would not be reassigned to a regular study visit since Study Day 28 is not within the 32-day window of any scheduled visit. Taper Visit assessments that are not reassigned will not be included in the tabulations but will be included in the data listings.

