5. All data listings should be sorted by treatment group (PBO first) with a page break between them, subject number, parameter (where appropriate), and study visit date/time where appropriate. If data for a subject and/or parameter is displayed on multiple lines, then display the subject number and/or parameter on only the first line. However, if the data for a subject or parameter is split between pages, then the subject number and parameter should be displayed on the page following the split.
6. For tables that summarize categorical (discrete) data, all categories between the maximum and minimum category should be presented in the table, even if there is a zero count for a particular category. A Missing category should be added to any variables to indicate missing information, if appropriate, but the percentages should be based on the number of subjects with non-missing categories.
7. If the categories are not ordered (eg, Medical History, Reasons for Discontinuation from the Study, etc.), then only those categories for which there is at least 1 subject represented in 1 or more groups should be included.
8. All fractional numeric values should be printed with a zero to the left of the decimal point (eg, 0.12, 0.3).
9. Missing descriptive statistics or p-values due to non-estimability in tables, as well as missing data in subject listings should be represented as either a hyphen (“-“) with a corresponding footnote (“ - = unknown or not evaluated”), or as “N/A” with the footnote “N/A = not applicable” whichever is appropriate.
10. Date values in the listings should be in the format ddMMMyyyy. If part of the date is unknown then leave it out; eg, APR2019. (In the unlikely event that the date and year are available but the month is not, insert a hyphen between the date and year.)
11. Any data listing for which there were no events should be produced, stating, “There were no events”

In addition, [Section 2.1.1](#) contains information on reporting precision.

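### Early stoppers who are not rated at Visit 5 and have no Taper Visit CGI-I from Day 88 on drop out of the Week 17 CGI-I percentages, and no missing-data analysis covers them

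*Protocol*

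**What the plan says.** - **Endpoint.** Protocol 9.7.2 lists as key secondary the "Clinical Global Impression of Improvement (CGI-I) at the last scheduled visit in the 17-week DB treatment phase", which is Visit 5, Week 17. SAP 1.2.2 lists CGI-I, by caregiver and clinician, among the ordinary secondary endpoints. SAP 7.1.3.4 tabulates the number and percentage of subjects at each of the seven scores.
- **Follow-up after stopping drug.** Protocol 4.5 says these subjects "will continue to be followed per protocol and at minimum maintain daily seizure eDiary entry until the double-blind phase is completed". Section 4.5.1 has the shorter form: they "will continue to record daily seizure frequency at minimum until the completion of the double-blind phase".
- **Early termination.** Protocol 7.2.3, whose list includes both CGI-I ratings, opens: "The following study procedures/assessments will be completed during the final double-blind visit or taper visit or at the time of early termination". The double-blind schedule (Table 1) has no early-termination column; the open-label schedule (Table 2) has one.
- **Off-drug data.** SAP 7.1 describes an estimand "where ALL randomized subjects would be included in this analysis throughout the study period" and adds that "all available data will be used, even if they were collected after the subject stopped taking study medication".
- **Taper Visit ratings.** SAP 7.1.1 moves them to the first later scheduled visit lying within 32 days. Otherwise: "Taper Visit assessments that are not reassigned will not be included in the tabulations but will be included in the data listings".
- **Missing values.** SAP 2.5 replaces missing data only where noted. The two imputation analyses in SAP 7.1.8 concern the primary endpoint.
- **Denominator.** SAP 12.1 item 6 allows a Missing category where appropriate, but "the percentages should be based on the number of subjects with non-missing categories".

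**The concern.** Each rule is ordinary by itself. Together they leave a gap. A subject who stops drug early can meet the stated minimum by keeping the diary, without a Week 17 CGI-I. If that subject was rated at an early Taper Visit, the rating is too far from Day 120 to stand in for Week 17. The subject then disappears from the percentages instead of appearing in them as unrated.

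The primary endpoint is protected by daily diary entry after drug is stopped and by two imputation analyses. CGI-I has neither. If subjects without a usable rating differ from those rated, or if the arms lose different numbers, the Week 17 percentages no longer compare the randomized groups. Unequal losses are conceivable. Protocol 1.2 reports rash leading to discontinuation in 6 GNX subjects and no PBO subjects across placebo-controlled studies, and somnolence of 33.9% v 5.6% in the fragile X trial. The second figure is an adverse-event rate, not an exit rate, and neither predicts exits in this trial.

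**Working it through.** **1. The SAP's own example.** The SAP puts Visit 5 on Day 120 (17 × 7 + 1) and Visit 4 on Day 64 (9 × 7 + 1). For a Taper Visit on Day 100, 120 − 100 = 20, inside 32 days; 100 − 64 = 36, outside. The rating goes to Visit 5, as SAP 7.1.1 states.

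**2. Where other Taper Visit ratings go.** The earliest day that can reach Week 17 is 120 − 32 = Day 88.
- Day 64 or earlier: Visit 3, Visit 4 or no visit, never Week 17.
- Days 65 to 87, with Visit 4 already done: no visit, so listed but not tabulated. On Day 87 the gap is 33 days.
- Day 88 onward: Week 17, if Visit 5 is the next scheduled visit.

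The example measures distance backwards as well as forwards. If a subject stopped before Visit 4 and missed it, a rating up to Day 96 (64 + 32) could be assigned to Visit 4. This does not bring any rating before Day 88 into Week 17.

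**3. How far reassignment reaches.** The documents give no dropout figure. *Assume* stopping days are uniform over Days 2 to 119 (118 days). If the Taper Visit falls on the stopping day, Days 88 to 119 qualify: 32/118 = 27%. If it falls 14 days later, stopping days 74 to 119 qualify: 46/118 = 39%. The other 61% to 73% of early stoppers have no Week 17 rating unless they attend Visit 5.

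**4. Effect on a difference in percentages.** The 50 per arm follows from 100 subjects at 1:1. *Assumed*: 40% (GNX) and 30% (PBO) much or very much improved among those rated, so 10 points observed-case. With mG and mP ratings missing and counted as not improved:

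difference = 0.40 × (50 − mG)/50 − 0.30 × (50 − mP)/50

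| Missing GNX v PBO | Calculation | Difference |
|---|---|---|
| 8 v 3 | 0.336 − 0.282 | 5.4 points |
| 4 v 4 | 0.368 − 0.276 | 9.2 points |
| 3 v 4 | 0.376 − 0.276 | 10.0 points |
| 3 v 8 | 0.376 − 0.252 | 12.4 points |

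The difference is unchanged when 0.40 × mG = 0.30 × mP. It shrinks when GNX loses more than that and grows when it loses less.

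**5. A second set of assumptions.** Take 50% v 30% among those rated (20 points), with 61% to 73% of early stoppers unrated as in step 3. With 15% GNX and 5% PBO stopping, the difference is 15.6 to 16.3 points; with 5% in each arm, 19.3 to 19.4. Nearly equal exits matter little.

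**The case against.** A reader might infer that only the diary is compulsory after stopping drug and that the Week 17 CGI-I is therefore a result in stayers alone. The documents do not support this. Protocol 4.5 keeps these subjects in follow-up per protocol, with the diary as a floor, so Visit 5 still applies. Protocol 7.2.3 asks for CGI-I at the taper visit or early termination. SAP 7.1 uses off-drug data, and SAP 7.1.1 brings Taper Visit ratings from Day 88 into Week 17. Only subjects missed by all these routes drop out, and nothing in the documents says they will be many.

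The consequence is also limited. Protocol 9.7 and SAP 7.1.7 confine testing to the primary endpoint, and under SAP 11 the SAP, which does not call CGI-I key, takes precedence. The visible plan contains no improved/not-improved split. Counts are reported, so with a Missing row a reader could rebuild the percentages over all subjects. Some neighbouring text is redacted. Counting every missing rating as not improved is a single unfavourable imputation, and observed-case percentages are a common choice for an untested ordinal scale.

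All of this stands, and it narrows the point without removing it. An early-termination rating before Day 88 is still not a Week 17 rating. The Missing row is optional and outside the denominator. Protocol 9.7 also plans point estimates with 95% confidence intervals for all endpoints, so the percentages will be read as a comparison.

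**Conclusion.** The point holds in a limited form. Early stoppers who are not rated at Visit 5 and have no Taper Visit CGI-I on or after Day 88 leave the Week 17 percentages, and no visible analysis examines what that does. This fits poorly with the SAP 7.1 aim of including all randomized subjects.

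Neither the size nor the direction can be fixed from the documents. Under the 40% v 30% assumption, a 10-point observed-case difference becomes anything from 5.4 to 12.4 points across the patterns shown, so a claim that the plan necessarily favours GNX would go too far. The primary analysis and its power are unaffected. This is a worthwhile correction to a descriptive endpoint that the protocol ranks as key secondary; it does not threaten the trial's main conclusion.

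**What to change.** 1. **Protocol 3.1, 4.5 and 4.5.1:** name the Week 17 CGI-I (clinician and caregiver, telephone allowed) beside the diary in the minimum follow-up for subjects who stop drug in the double-blind phase.
2. **SAP 7.1.3.4:** add a CGI-I table over all ITT subjects with a Missing row inside the denominator, shown beside the observed-case table. Count missing as not improved only in a sensitivity summary.
3. **SAP 7.1.1, in the same edit:** say whether reassignment applies to subjects who stop drug but stay in the study, since the section speaks of leaving the study while Protocol 4.5 speaks of stopping drug. Also check the Day 28 example, which finds no scheduled visit within the window although Week 5 (Day 36) is 8 days later.

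The cost is two short ratings per early stopper, one extra table and a few sentences. The percentages over all ITT subjects may look slightly less favourable than the observed-case ones.

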4.5.2. Reasons for Early Discontinuation

The reason for early discontinuation must be determined by the investigator and recorded in the subject's source documents and on the eCRF. If a subject is withdrawn for more than 1 reason, each reason should be documented in the source document and the most clinically relevant reason should be entered on the eCRF.

Reasons for early termination include but are not limited to the following:

- Adverse event in which the character, severity or frequency is new in comparison to the patient's existing risk profile with the exception of seizures.
- An Adverse Event that is associated with non-reversible target organ dysfunction, with the associated laboratory abnormalities as defined in exclusion criteria 11, 12 or 13. An allowance may be made for continued treatment if the abnormality is not medically significant (non-life-threatening or does not require ongoing treatment that could be life-threatening)
- A laboratory abnormality or vital sign change that is irreversible and considered medically significant, associated with use of the investigational product
- Protocol violation/protocol deviation
- Withdrawal by subject or parent/LAR
- Lost to follow-up
- Lack of efficacy
- Death
- Physician decision
- Pregnancy

- Other (must be specified in the subject source document and eCRF)

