10. Have any disease or condition (medical or surgical; other than CDKL5) at screening that might compromise the hematologic, cardiovascular, pulmonary, renal, gastrointestinal, or hepatic systems; or other conditions that might interfere with the absorption, distribution, metabolism, or excretion of the investigational product, or would place the subject at increased risk.
11. An AST (serum glutamic oxaloacetic transaminase [SGOT]) or ALT (serum glutamic pyruvic transaminase [SGPT]) greater than 3 times the upper limit of normal (ULN) at study entry. If AST or ALT increases > 3 times ULN during the study, subject should be followed with weekly laboratory repeat testing and continue in study if levels trending down. Subject will be discontinued if levels do not decline to under 3 x ULN.
12. Total bilirubin levels greater than ULN at study entry. In cases of documented, stable medical condition (i.e., Gilbert's Syndrome) resulting in levels of total bilirubin greater than ULN, the medical monitor can determine if a protocol exception can be made. If total bilirubin increases to 1.5 x ULN or more during study, the subject will be discontinued.
13. Subjects with significant renal insufficiency, estimated glomerular filtration rate (eGFR) < 30 mL/min (calculated using the Cockcroft-Gault formula, Pediatric GFR calculator or Bedside Schwartz), will be excluded from study entry or will be discontinued if the criteria is met post baseline.
14. Have been exposed to any other investigational drug within 30 days or less than 5 half-lives prior to screening.
15. Unwillingness to withhold grapefruit, Seville oranges or star fruit from diet during the entire clinical trial.
16. Unwillingness to withhold alcohol throughout the entire clinical trial.
17. Have active suicidal plan/intent or have had active suicidal thoughts in the past 6 months or a suicide attempt in the past 3 years.
18. Known sensitivity or allergy to any component in the investigational product(s), progesterone or other related steroid compounds.

19. Plasma allopregnanolone – sulfate (Allo-S) levels ≥ 6.0 ng/ml at the screening visit.

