7.6.5. Clinical Laboratory Tests

Laboratory safety assessments will be collected at every clinic visit throughout the study to monitor subject safety. Clinical laboratory tests are listed in [Section 12.2](#) will be collected per the schedule listed in [Table 1](#) and [Table 2](#). These clinical laboratory assessments will include CBC with automated differential, creatinine, blood urea nitrogen, and eGFR calculation, comprehensive metabolic panel, as well serum pregnancy test for all women of childbearing potential.

The following liver function and eGFR tests will be monitored throughout the study as follows.

- If AST or ALT increases > 3 times ULN during the study, subject should be followed with weekly laboratory repeat testing and continue in study if levels trending down. Subject will be discontinued if levels do not decline to under 3 x ULN.
- If total bilirubin increases to 1.5 x ULN or more during study, the subject will be discontinued.

- Subjects with significant renal insufficiency, eGFR < 30 mL/min (calculated using the Cockcroft-Gault formula or Pediatric GFR calculator or Bedside Schwartz) will be discontinued if the criterion is met post baseline.

If any of the criteria above are deemed clinically significant by the investigator, then the sponsor's medical monitor should be contacted.

Due to the difficulty in obtaining urine samples, urinalysis will be conducted at Visit 1 (screening) or baseline (Visit 2), Week 17 (Visit 5), Week 52 (Visit 9), and annually thereafter or at the safety follow up visit if investigational product is discontinued. An attempt will be made to collect a urine sample at screening in order to perform the study-related urinalysis. Otherwise, the urine sample for the urinalysis can be collected at baseline.

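### Section 4.5.2 allows treatment to continue, if an abnormality is judged not medically significant, at the liver and kidney limits where Sections 4.2 and 7.6.5 require stopping

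*Protocol*

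**What the plan says.** Protocol Section 4.2, criteria 11 to 13, sets entry limits and also on-study stopping limits. Section 7.6.5 repeats the on-study limits, and so does the synopsis in its exclusion criteria.

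- **Bilirubin:** "If total bilirubin increases to 1.5 x ULN or more during study, the subject will be discontinued" (7.6.5). The entry limit is lower: "Total bilirubin levels greater than ULN at study entry" (4.2, criterion 12).
- **eGFR below 30 mL/min:** such subjects "will be excluded from study entry or will be discontinued if the criteria is met post baseline" (4.2, criterion 13).
- **AST/ALT above 3 x ULN:** weekly retesting, and the subject stays in while values fall. Then: "Subject will be discontinued if levels do not decline to under 3 x ULN" (7.6.5).

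Section 4.5.2 lists reasons for early termination. One is an adverse event with "non-reversible target organ dysfunction, with the associated laboratory abnormalities as defined in exclusion criteria 11, 12 or 13". The same bullet goes on: "An allowance may be made for continued treatment if the abnormality is not medically significant". A parenthesis explains the condition: the abnormality is not life-threatening, or it does not call for continuing treatment that might itself be life-threatening.

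**The concern.** Sections 4.2 and 7.6.5 leave no room for judgement once a limit is reached. Section 4.5.2 takes the same criteria, in the more serious setting of non-reversible organ dysfunction, and brings in a judgement that can keep the subject on drug. Two investigators with the same result could act differently, and each could cite the protocol.

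What is at stake is subject safety and uniform conduct, in a mainly paediatric trial with up to 50 sites and about 3 years of open-label dosing. Hepatic and renal stopping limits should have a single meaning.

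**Working it through.** No figure in the plan needs to be reproduced. The thresholds agree: Sections 4.2 and 7.6.5 give the same limits, and 4.5.2 refers to them by criterion number. The disagreement is about the action. The table sets the rules side by side for each situation.

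| On-study finding | 4.2, synopsis, 7.6.5 | 4.5.2 | Conflict? |
|---|---|---|---|
| Bilirubin above ULN but below 1.5 x ULN | No mandatory stop; ULN is the entry limit | Nothing to contradict | No |
| AST/ALT above 3 x ULN and falling | Weekly retest, continue | Nothing to contradict | No |
| A stopping limit reached, dysfunction reversible | Stop | Allowance not engaged | No |
| A stopping limit reached, dysfunction non-reversible, judged medically significant | Stop | Reason for termination; allowance not available | No |
| A stopping limit reached, dysfunction non-reversible, not life-threatening (for example eGFR 28 mL/min) | Stop | Continued treatment may be allowed | **Yes** |

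Three further checks.

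1. *How wide is the condition?* The two parts of the parenthesis are joined by 'or', so meeting either is enough. Being non-life-threatening alone qualifies, and that could cover much non-reversible liver or kidney impairment.
2. *Is the result coherent?* Compare the third and fifth rows. A transient bilirubin of 1.5 x ULN must stop under 7.6.5. Non-reversible dysfunction at the same bilirubin may continue under 4.5.2. The less serious case gets the stricter rule, which is unlikely to be intended.
3. *Does any text decide between the rules?* None found. Section 4.5.2 does not say that it overrides the stopping limits, and neither 4.2 nor 7.6.5 refers to it. The Gilbert's Syndrome exception in criterion 12 follows the entry limit, and the on-study stopping sentence comes after it without qualification. SAP Section 11 ranks the SAP over the protocol, not one protocol section over another. The potentially clinically significant thresholds in SAP Section 9.2 are for reporting.

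**The case against.** The best defence is that 4.5.2 names criteria 11 to 13 and then states an allowance, so it can be read as a specific exception to a general rule. Section 7.6.5 itself refers to clinical significance after its stopping rules. That reading is possible, but the significance clause in 7.6.5 only triggers contact with the medical monitor. It does not soften the stopping rules and does not ask for approval to continue. A site working from 7.6.5 would have no reason to know that an exception exists.

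A second defence is the next bullet in 4.5.2, which makes an irreversible, medically significant, drug-associated laboratory abnormality a reason for termination. Criterion 13 itself describes eGFR below 30 mL/min as significant renal insufficiency, so many investigators would stop the subject in the example. This stands as far as it goes. But it confirms that under 4.5.2 the outcome depends on a judgement of significance, which 4.2 and 7.6.5 do not allow.

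It could also be said that 4.5.2 only lists reasons to record. Most of it does, but the allowance sentence is operative, because it permits treatment.

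Three stronger readings may tempt a reader, and the documents do not support them.

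- *That 4.5.1 also makes stopping optional.* It says "The investigator may discontinue subjects from the clinical study for any of the following reasons" and includes a subject who "no longer meets the inclusion criteria or develops any of the exclusion criteria". This is a general list of grounds. It also contains withdrawal of consent, which is not at the investigator's discretion. Pregnancy is an exclusion criterion and so falls under the same bullet, yet Section 8.1.6 makes withdrawal compulsory. Specific mandatory rules can sit beside this list without contradiction.
- *That 4.5.2 permits treatment through any non-reversible organ dysfunction.* It does so only where the abnormality is judged not medically significant.
- *That the lack of a retest interval for bilirubin and eGFR is a gap.* Breaches of those limits lead straight to stopping, so no watch-and-wait schedule is needed as it is for AST/ALT. Laboratory tests are also done at every clinic visit.

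**Conclusion.** The conflict is real, sits in current protocol text, and is minor. It is confined to 4.5.2 against 4.2 (criteria 11 to 13), the synopsis and 7.6.5, and to one situation: a stopping limit is reached, the adverse event involves non-reversible organ dysfunction, and the abnormality is judged not medically significant.

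Few subjects are likely to meet all three conditions, but the number cannot be computed. The nearest figures are in protocol Section 1.2: AST/ALT above 3 x ULN in 0.3% of GNX and 0.5% of placebo subjects, pooled over completed placebo-controlled studies. A reader might turn these into a chance of seeing a case. That would count a different event, because the rates include rises that later fall and say nothing about reversibility or judged significance. The documents give no rate for bilirubin at 1.5 x ULN or for eGFR below 30 mL/min.

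The effect on the primary analysis is small. Subjects who stop drug during the double-blind phase are to keep the seizure diary (protocol Section 4.5), and SAP Section 7.1 uses data collected after drug is stopped. This assumes that diary-keeping continues as instructed.

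**What to change.** In 4.5.2, delete the allowance sentence with its parenthesis, and state that the limits in 4.2 (criteria 11 to 13) and 7.6.5 govern stopping of investigational product.

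If the sponsor does want an exception, write it once, in 7.6.5, with medical monitor approval and defined repeat testing. Cross-refer to it from the synopsis, 4.2 and 4.5.2; if the synopsis were left out, the contradiction would remain there.

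The preferred version costs one deleted sentence and one added cross-reference. Section 4.5.1 needs no edit, and 7.6.5 changes only if an exception is wanted. Sample size and the primary analysis are unaffected.
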